Interim analyses: Not applicable

V. FLOW CHART AND SCHEDULE OF ASSESSMENTS

Flow Chart

- *1: 28 days after final study treatment, or before starting other study drugs, or before starting other treatment for prostate cancer, whichever comes first
- *2: Subjects who discontinued the 1st line AAT due to PSA progression will start the 2nd line AAT within 6 weeks after the date of examination that identified PSA progression. Subjects who discontinued the 1st line AAT due to other reasons will start the 2nd line AAT within 6 weeks from the day when the investigator or subinvestigator decided the discontinuation.

Table 1: Schedule of Assessments

1st line AAT

	Screening period				1st line AAT		Unscheduled*a
Visit Days	Days -28 to -7	1	29	57	85 and every subsequent 84 days	113 and every subsequent 28 days	_
Visit Weeks	-4 to -1	1	5	9	13 and every subsequent 12 weeks	17 and every subsequent 4 weeks	_
Allowed visit window (days)	-	-	± 7	± 7	± 7	± 7	_
Informed consent ^{*b}	X *b						
Subject background survey	Х						
Confirmation of in/exclusion criteria	Х	Х					
Randomization/enrollment		X *c					
Vital signs ^{*d}	Х	Х	Х	Х	Х	Х	Х
Height/body weight	Х						
Laboratory tests ^{*e}	Х	Х	Х	Х	Х	Х	Х
PSA	Х	Х			Х	Х	Х
Abdominopelvic CT/MRI and bone scintigraphy (every 3 months)	X ^{*f}				Х		Х
Chest CT	X^{*f}				X^{*g}		Х
ECOG Performance Status	Х	Х	Х	X	Х	Х	Х
FACT-P		Х			Х		
EQ-5D-5L		Х			Х		
Brief Pain Inventory-Short Form (BPI-SF) ^{*h}	Х	X			Х		
Brief Fatigue Inventory (BFI)	Х	Х			Х		
Adverse event survey ^{*i}		Х	Х	Х	Х	Х	Х
Survey on previous/concomitant medication	Х	X	X	Х	Х	Х	Х
Study drug prescription (every month)		Х	Х	Х	Х	Х	

CT: Computed Tomography, ECOG: Eastern Cooperative Oncology Group, FACT-P: Functional Assessment of Cancer Therapy-Prostate

*a: Unscheduled visit may be made whenever adverse events should be assessed, or PSA progression and disease progression should be confirmed. Laboratory tests, PSA measurement, and diagnostic imaging will be performed when assessment is required.

*b: Informed consent will be obtained within 42 days before enrollment (Day 1) and before initiating the scheduled study procedures.

*c: Randomization should be performed on Day 1 after the confirmation of eligibility.

Sponsor: API

- *d: Measure vital signs (blood pressure and pulse rate) at each visit.
- *e: Laboratory tests include hematology, biochemistry, blood glucose test, and urinalysis.

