7.1 Sample Size

The number of evaluable subjects will be approximately 200 subjects (1st line AAT enzalutamide group: 100, 1st line AAT flutamide group: 100).

The sample size to evaluate the time to PSA progression with 1st line AAT (TTPP1), which is the primary endpoint of the study, was calculated in consideration of the following points:

- Median TTPP1 with enzalutamide: 10.5 months.
- Median TTPP1 with flutamide: 6 months. Values reported in the literature: 5 months according to [Okihara et al., 2007], 6.25 months according to [Narimoto et al., 2010].
- The ratio of randomization of 1st line AAT enzalutamide and flutamide groups is 1:1.
- Subject enrollment period is 12 months, and the observation period is 24 months from the enrollment of the last subject.
- Type I error of the two-sided test is 0.05, and power is 90%.
- A log-rank test with the TTPP1 parameters shown above requires 135 events. The necessary number of subjects calculated based on the required number of events is 74 subjects per group.

Required number of events and necessary number of subjects above are calculated with the formulas below based on [Schoenfeld, 1983]. The codes in the formulas are defined as follows.

 M_t : Median TTPP1 in enzalutamide group

 M_c : Median TTPP1 in flutamide group

 t_a : Enrollment period

 t_f : Observation period from the last subject enrollment

 $Z_{1-\alpha}$: 1- α % point of standard normal distribution

 $Z_{1-\beta}$: 1- β % point of standard normal distribution

[figure not shown]
Hazard in enzalutamide group $(H_t) = \frac{\log_e 2}{M_t}$ Hazard in flutamide group $(H_c) = \frac{\log_e 2}{M_c}$ Hazard ratio for enzalutamide group/flutamide group $(HR) = \frac{H_t}{H_c}$ Required number of events $(N_d) = \frac{4 \times (Z_{1-\alpha} + Z_{1-\beta})^2}{(\log_e HR)^2}$ *The number after the decimal point will be rounded up to the nearest integer. Incidence of events of enzalutamide group $(P_t) = 1 - \frac{1}{6} \left(\exp(-H_t \times t_f) + 4 \times \exp\left(-H_t \times (t_f + \frac{1}{2} \times t_a)\right) + \exp\left(-H_t \times (t_f + t_a)\right) \right)$ Incidence of events of flutamide group

$$(P_c) = 1 - \frac{1}{6} \left(\exp\left(-H_c \times t_f\right) + 4 \times \exp\left(-H_c \times (t_f + \frac{1}{2} \times t_a)\right) + \exp\left(-H_c \times (t_f + t_a)\right) \right)$$

Incidence of events of both groups $(P) = \frac{1}{2} \times (P_t + P_c)$

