7.10 Handling of Missing Data, Outliers, Visit Windows, and Other Information

As a general principle, no imputation of missing data will be done. Exceptions are the start and stop dates of AEs and concomitant medication. The imputed dates will be used to allocate the concomitant medication and AEs to a treatment group, in addition to determining whether an AE is/is not treatment emergent. Listings of the AEs and concomitant medications will present the actual partial dates; imputed dates will not be shown. Subjects who do not receive the study drug to which they have been randomized will be analyzed as treated.

See the SAP for details of the definitions for windows to be used for analyses by time point.

Sites that do not enroll at least 10 subjects will be pooled for analyses by site. The pooling decisions will be made and documented prior to study database hard-lock. The handling of outlier is specified by the SAP. The acceptable time range for study visit is specified by "VI. ACCEPTABLE RANGE OF SCHEDULE OF ASSESSMENTS." Values that fall out of the range will be excluded. Convention of censoring for each endpoint are defined in the table below.

	TTPP1	TTPP2	2nd TTPP	Time to PSA 50%/90% decline	TTF1	TTF2	rPFS	MFS
Subjects without PSA value at baseline or in observation period	Considered as censoring at randomization	Considered as censoring at randomization	Excluded from analysis	Considered as censoring at randomization	Not considered as censoring *To be judged based on continuation of study treatment	Not considered as censoring *To be judged based on continuation of study treatment	Not considered as censoring *To be judged based on result of radiographic assessment	Not considered as censoring *To be judged based on result of radiographic assessment
Subjects without the result of radiographic assessment at baseline or in observation period	Not considered as censoring *To be judged based on result of PSA measurement	Not considered as censoring *To be judged based on result of PSA measurement	Not considered as censoring *To be judged based on result of PSA measurement	Not considered as censoring *To be judged based on result of PSA measurement	Not considered as censoring *To be judged based on continuation of study treatment	Not considered as censoring *To be judged based on continuation of study treatment	Considered as censoring at randomization	Considered as censoring at randomization

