7 STATISTICAL METHODOLOGY

7.1 General Considerations

7.1.1 General Principles

For continuous variables, descriptive statistics will include the number of subjects (n), mean, standard deviation, median, minimum and maximum. When needed, the use of other percentiles (e.g.10%, 25%, 75% and 90%) will be mentioned in the relevant section. Frequencies and percentages will be displayed for categorical data. A missing category will be added to categorical variables where data is missing.

Summaries based on ITT (e.g. disposition, baseline and efficacy data) will be presented by planned treatment group, unless specifically stated otherwise. Safety analysis and other summaries based on SAF will be presented by actual treatment received.

All statistical comparisons will be made using two sided tests at the α =0.05 significance level unless specifically stated otherwise. All null hypotheses will be of no treatment difference, all alternative hypotheses will be two-sided, unless specifically stated otherwise.

All data processing, summarization, and analyses will be performed using SAS® Version 9.4 or higher on Windows. Specifications for table, figures, and data listing formats can be found in the TLF specifications for this study.

The Age (Derived) variable from EDC will be used for analysis. If date of birth is incomplete, the variable Age from EDC will be used for analysis.

Year will be calculated as (days/365.25) rounded up to 1 significant digit.

Month will be calculated as (days/30.4375) rounded up to 1 significant digit.

Time to event or duration of event endpoints will be based on the actual date rather than Visit Day.

For the definition of subgroups of interest please refer to section 7.8.

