Subjects who miss PSA data at least twice consecutively at scheduled PSA measurement points	Considered as censoring at final PSA measurement before missing data occur	Considered as censoring at final PSA measurement before missing data occur	Subjects who continue the first study drug are excluded from analysis Subjects who have shifted to the second study drug are considered as censoring at final PSA measurement before missing data occur	Considered as censoring at final PSA measurement before missing data occur	Not considered as censoring *To be judged based on continuation of study treatment	Not considered as censoring *To be judged based on continuation of study treatment	Not considered as censoring *To be judged based on result of radiographic assessment	Not considered as censoring *To be judged based on result of radiographic assessment
Subjects who miss radiographic assessment at least twice consecutively at scheduled radiographic assessment points	Not considered as censoring *To be judged based on result of PSA measurement	Not considered as censoring *To be judged based on result of PSA measurement	Not considered as censoring *To be judged based on result of PSA measurement	Not considered as censoring *To be judged based on result of PSA measurement	Not considered as censoring *To be judged based on continuation of study treatment	Not considered as censoring *To be judged based on continuation of study treatment	Considered as censoring at final radiographic assessment before missing data occur	Considered as censoring at final radiographic assessment before missing data occur

Sponsor: Astellas Pharma Inc. SAP Version 1.00

ISN/Protocol 9785-MA-3051

7.4.4 **Analysis of Other Variables**

PSA measurement

Descriptive statistics for PSA measurement and its change from baseline will be summarized at by visit and treatment group. These measurement value and change from baseline will be plotted as mean +/- SD plot.

Swimmer's plot

Swimmer's plot will be made to present treatment flow and event occurrence for each patient. This plot will include time on and off of the 1st/2nd line AAT continuations as a bar chart, and the points at which drug related AEs (by CTCAE grades), PSA progression, radiographic progression, PSA response, and death.

7.5 **Analysis of Safety**

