Screening visit	−28 days to −7 days	28 days to 7 days before randomization
Week 1 (Day 1)	1	-
Week 5 (Day 29)	29	Reference date \pm 7 days
Week 9 (Day 57)	57	Reference date \pm 7 days
Week 13 (Day 85)	85	Reference date \pm 7 days
Every subsequent 4 weeks	Every subsequent 28 days	Reference date ± 7 days

2nd line AAT

Study Visit	Reference Date	Acceptable Range
Week 1 (Day 1)	1	-
Week 5 (Day 29)	29	Reference date \pm 7 days
Week 9 (Day 57)	57	Reference date \pm 7 days
Week 13 (Day 85)	85	Reference date \pm 7 days
Every subsequent 4 weeks	Every subsequent 28 days	Reference date ± 7 days
At completion or discontinuation	Day of completion or discontinuation visit	Reference date + 7 days
Safety follow-up	Final study treatment + 28 days	Reference date ± 7 days

The value which assessment day is the closest to the defined target day within these windows is used. If two values are equally close, the earlier is used in the analysis. Note that a value which is assessed prior to Day 1 of the 1st line AAT or 2nd line AAT will be available as baseline assessment once it is investigated and approved by the review board. Also, a value which is assessed as Day 1 of the 2nd line AAT will be utilized as end/discontinuation of 1st line AAT when a subject start 2nd line AAT without confirmation of PSA progression or because of other than PSA progression.

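### The protocol excludes out-of-window PSA values without exempting TTPP1, and neither document says which PSA values feed the PSA time-to-event endpoints

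*Protocol*

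**What the plan says.** - **Exclusion.** Protocol 7.10 refers to the ranges in Section VI and states: "Values that fall out of the range will be excluded". The sentence that follows introduces the censoring table for TTPP1 and the other time-to-event endpoints.
- **Ranges.** Section VI opens with efficacy tests, PSA first: Day 85, Day 113, then every 28 days, each ±7 days. The 1st line table has no row for unscheduled PSAs and none for completion or discontinuation.
- **One value per window.** SAP 7.11.3 repeats these PSA windows and adds: "The value which assessment day is the closest to the defined target day within these windows is used". It does not repeat the exclusion sentence.
- **Unscheduled PSAs.** Protocol Table 1, footnote a: "Unscheduled visit may be made whenever adverse events should be assessed, or PSA progression and disease progression should be confirmed".
- **Confirmation.** Protocol 5.3.1.1 and SAP 6.1.1 ask for a second value at least 3 weeks later when PSA had declined at Week 13. For subjects without such a decline they state no confirmation requirement.
- **Missed PSAs.** SAP Table 7-1 has a row for "Subjects who miss PSA data at least twice consecutively at scheduled PSA measurement points". For TTPP1 these subjects are censored at the last PSA before the gap.
- **Dates.** SAP 7.1.1: "Time to event or duration of event endpoints will be based on the actual date rather than Visit Day".

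**The concern.** TTPP1 is built from individual PSA values: the nadir, the first qualifying rise and, for some subjects, a confirming value. The plan has to say which values are eligible. The only eligibility rule it states is the protocol exclusion, and that rule is unqualified. A programmer who follows it would discard valid central-laboratory results, including results from visits that the protocol permits in order to confirm progression.

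The consequence is more than lost precision. Subjects who progress are to switch drug within 6 weeks of the examination that identified progression. If the confirming value is discarded and the subject has already switched, the progression definition may not be met in the analysis data. Table 7-1 then censors the subject at the last PSA before discontinuation. Such censoring falls on subjects whose PSA is rising, in an open-label trial, so it could not be assumed non-informative.

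**Working it through.** **Plan's own figure.** Inputs from Protocol 7.1: "Median TTPP1 with enzalutamide: 10.5 months"; "Median TTPP1 with flutamide: 6 months"; two-sided 0.05; 90% power; 12 months' accrual and 24 months' further observation.

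- HR = 6/10.5 = 0.571, and ln HR = −0.5596.
- Events = 4 × (1.960 + 1.2816)² / 0.5596² = 134.2, rounded up to 135.
- The protocol's event-probability formula gives 0.858 (enzalutamide) and 0.966 (flutamide), mean 0.9122. Then 135/(2 × 0.9122) = 73.99, or 74 per group, and 74/0.75 = 98.7, or about 100.

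The plan's figures reproduce, and nothing below changes them.

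**Window coverage.** A ±7-day window spans 15 days and scheduled PSAs are 28 days apart. From Day 106, 15/28 = 53.6% of days are inside a PSA window and 13/28 = 46.4% are outside. Days 2 to 77 have no PSA window.

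**Confirming draw.** Let the rise be found d days from its reference date (d = −7 to +7, 15 possible days) and the confirming draw be taken k days later. The next window runs from +21 to +35 days after the first reference date. For k from 21 to 28 the draw is out of window when d + k < 21.

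| Interval k | Detection days lost | Count |
|---|---|---|
| 21 days | d = −7 to −1 | 7 of 15 |
| 24 days | d = −7 to −4 | 4 of 15 |
| 28 days | none | 0 of 15 |

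Example: a rise on Day 110 (window 106–120), confirmed on Day 131, falls before the next window (134–148).

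**One value per window.** Two values at least 21 days apart cannot share a 15-day window, so this rule alone cannot break a confirming pair. If two PSAs fall in one window, it can drop the one that was the nadir or the earlier rise.

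**Two consecutive out-of-window PSAs.** This matters only if an excluded value counts as missed. Let q be the chance that a scheduled PSA is out of window, independent across visits (both assumed). Let a and b be the probabilities of no run of two so far with the last visit in or out of window, starting at a = 1, b = 0. At each visit a becomes (a + b)(1 − q) and b becomes (previous a) × q; P(run) = 1 − a − b. Nine PSA visits reach Day 85 + 8 × 28 = 309, close to the assumed enzalutamide median (10.5 × 30.4375 = 320 days). Four visits reach Day 169, close to the flutamide median (6 × 30.4375 = 183 days).

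| Assumed q | 4 visits | 9 visits |
|---|---|---|
| 2% | 0.1% | 0.3% |
| 5% | 0.7% | 1.9% |
| 10% | 2.8% | 7.2% |

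**Power, if events were lost and not replaced (assumed).** Power = Φ(√events × 0.5596/2 − 1.960). With 135 events this is 90.2%; with 128 (5% lost) 88.6%; with 122 (10% lost) 87.1%. The TTPP1 cut-off waits for at least 135 events, so lost events may delay the cut-off before they cost power.

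**The case against.** The best reply is that the plan plainly intends all dated PSAs to be used.

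- Protocol 7.10 itself describes the SAP windows as serving time-point analyses.
- SAP 7.1.1 works from actual dates, and SAP 7.4.1 dates progression at the first day on which the definition is met.
- The waterfall plots in SAP 7.4.2.2 set aside PSAs within 3 weeks of baseline. That carve-out would be pointless if only in-window values counted, since the first window opens on Day 78.
- SAP 7.11.3 lets the 2nd line Day 1 value stand as the end-of-1st-line value when a subject switches without confirmed PSA progression.
- SAP 7.11 refers to a data specification document, not available here, that may settle the matter.

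This shows likely intent, but it does not close the gap. The time-point remark describes the SAP's windows; the exclusion sentence refers to protocol Section VI and carries no such limit. SAP 7.1.1 governs which date is used, not which values are eligible. The statement in SAP 7.11.2 that all values are included sits under outliers; read more broadly, it contradicts Protocol 7.10. It is unclear whether the 2nd line Day 1 allowance covers a subject whose progression was confirmed at the site by a value that the analysis then excludes. A rule that decides primary-endpoint events belongs in the SAP itself.

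The objection does limit the size. The next on-schedule draw, 28 days after the rise, always falls in a window. A later in-window PSA could still confirm, and the event would keep its first date. The protocol permits unscheduled confirming visits but does not say that they are common.

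**Conclusion.** The point holds as an unqualified rule with an unresolved scope. Followed literally, Protocol 7.10 removes valid PSAs from TTPP1 and the other PSA time-to-event endpoints, and no passage prevents that. The exposed cases are off-window or unscheduled values that set the nadir, the first rise or the confirmation. The confirmation risk applies only after a Week 13 decline and to draws taken sooner than the usual 28 days: 7 of 15 detection days at 21 days, 4 of 15 at 24. The main harm is shifted event dates and possibly informative censoring; an effect on power is secondary.

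A reader might infer three stronger things that the documents do not support:

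- That keeping one value per window destroys confirmations. It cannot, because the pair is at least 21 days apart.
- That a late visit leads to censoring. The trigger is two consecutive misses, and neither document equates an excluded PSA with a missed one.
- That a large share of subjects would be affected. The documents give no out-of-window rate. The 0.3% to 7.2% over 9 visits rests on assumed, independent rates of 2% to 10% and on the unsettled reading of a missed PSA.

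**What to change.** 1. In SAP 7.11.3, state that the windows and the Protocol 7.10 exclusion apply only to by-visit summaries, including the Week 13 response.
2. State that TTPP1, TTPP2, 2nd TTPP, time to 50% PSA decrease, nadir, confirmation and best PSA response use every central-laboratory PSA by actual date, including unscheduled ones.
3. In Table 7-1, count a scheduled PSA as missed only if none was drawn in a stated interval around it, for example from midpoint to midpoint between adjacent scheduled dates.
4. Record this as a change from Protocol 7.10, either justified in the clinical study report or made by protocol amendment. Because the protocol sentence is affected, SAP wording alone is not enough.

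The cost is wording and one documented departure from the protocol. No new data are needed, and the 135 events and 100 subjects per group stay as they are.

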5.3.2.1 Radiographic Progression-Free Survival (rPFS)

rPFS is defined as the period from randomization to the time when radiographic disease progression is observed or death of any cause during the study period, whichever occurs earlier. With regard to radiographic disease progression, soft tissue lesion will be defined by RECIST guidelines version 1.1 (RECIST 1.1), bone lesion will be defined as the occurrence of at least 2 new bone lesions confirmed by bone scintigraphy in line with PCWG2 recommendation. Evaluation will be made in subjects with distant metastasis at baseline.

The following are procedures necessary for confirmation of radiographic disease progression.

Study visit where disease progression is observed	Criteria for disease progression	Criteria for confirmation of disease progression (necessity for imaging for confirmation and time of confirmation)	Criteria for imaging for confirmation of disease progression
Visits up to Week 13 of 1st line AAT	Bone lesion: ≥2 new bone lesions in comparison with baseline bone scintigraphy by PCWG2 Soft tissue lesion: Disease progression detected by CT or MRI, and defined by RECIST 1.1	Timing: ≥6 weeks after disease progression confirmed or at Week 25 Visit No need of imaging for confirmation	≥2 new bone lesions in comparison with bone scintigraphy at Week 13 of 1st line AAT N/A
Visits after	Bone lesion: ≥2 new bone lesions in comparison with bone scintigraphy at Week 13* of 1st line AAT	No need of imaging for confirmation	N/A
Week 13 of 1st line AAT	Soft tissue lesion: Disease progression detected by CT or MRI, and defined by RECIST 1.1	No need of imaging for confirmation	N/A

*: Compare with baseline bone scintigraphy if data from Week 13 are missing.

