5.3.2.2 Metastasis-Free Survival (MFS)

MFS is defined as the period from randomization to new radiographic metastatic lesion or death of any cause during the study period, whichever occurs earlier. Evaluation will be made in subjects in whom distant metastasis is not confirmed at baseline.

5.3.2.3 Objective Response Rate (ORR) in Best Overall Soft Tissue Response of RECIST Guidelines with 1st Line AAT

According to RECIST 1.1, the investigator or sub-investigator will evaluate the overall response in target, non-target, and new lesions in soft tissue at each time point. At the end of the 1st line AAT period, the best overall response will be assessed. Of subjects with measurable soft tissue lesion (at least 1 target lesion according to RECIST 1.1) in baseline imaging, the proportion of subjects with objective response (complete or partial response) will be evaluated.

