Subjects without PSA progression at final data cut-off (Including cases inconsistent with PSA progression defined by the protocol)	Subjects who continue the first study drug are considered as censoring at final PSA measurement	Considered as censoring at final PSA measurement	Subjects who continue the first study drug are excluded from analysis Subjects who have shifted to the second study drug are considered as censoring at final PSA measurement	Considered as censoring at final PSA measurement	Not considered as censoring *To be judged based on continuation of study treatment	Not considered as censoring *To be judged based on continuation of study treatment	Not considered as censoring *To be judged based on result of radiographic assessment	Not considered as censoring *To be judged based on result of radiographic assessment
Subjects without radiographic progression at final data cut-off (Including cases inconsistent with progression defined by the protocol)	Not considered as censoring *To be judged based on result of PSA measurement	Not considered as censoring *To be judged based on result of PSA measurement	Not considered as censoring *To be judged based on result of PSA measurement	Not considered as censoring *To be judged based on result of PSA measurement	Not considered as censoring *To be judged based on continuation of study treatment	Not considered as censoring *To be judged based on continuation of study treatment	Considered as censoring at final radiographic assessment	Considered as censoring at final radiographic assessment

	TTPP1	TTPP2	2nd TTPP	Time to PSA 50%/90% decline	TTF1	TTF2	rPFS	MFS
Death during the study	Subjects who died during treatment with the first study drug are considered as censoring at final PSA measurement before death	Considered as censoring at final PSA measurement before death	Subjects who died during treatment with the first study drug are excluded from analysis Subjects who died during treatment with the second study drug are considered as censoring at final PSA measurement before death	Considered as censoring at final PSA measurement before death	The event is considered to occur at the time of death	The event is considered to occur at the time of death	The event is considered to occur at the time of death	The event is considered to occur at the time of death

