7.4.1 Analysis of Primary Endpoint

The primary efficacy analysis will be performed on the TTPP1 for the subjects in the ITT population. TTPP1 is the period from randomization to the first day when PSA progression is objectively identified. Convention of censoring is specified in table 7-1.

If a subject meets the criteria for more than one censoring rule, they will be censored with the earliest censoring date. The PSA progression date is the first date where progression definition is met, not confirmed.

Methodology

The benefit of enzalutamide as compared to flutamide will be assessed with the stratified log-rank test as the primary efficacy analysis. The stratification factor will be the disease stages (M0/N0, M0/N1, or M1) used as stratification factor for allocation.

The hypothesis for comparisons is as follows:

H0: The survival time distribution of enzalutamide group is the same as that with flutamide group.

H1: The survival time distribution of enzalutamide group is not the same as that with flutamide group.

The significance level is 0.05 (two-sided). ITT is used for the primary analysis.

Unstratified Cox's Proportional Hazards Model with treatment and disease stage as the covariate will be used to support the log rank test.

The benefit of enzalutamide compared to flutamide will be evaluated by hazard ratio (enzalutamide/flutamide) with its 95% confidence interval (CI) based on Cox Proportional Hazard Model.

Kaplan-Meier curves will be used to estimate the distribution of duration of TTPP1 and Stratified curve will be estimated by disease stage. The 50th percentile of Kaplan-Meier estimates will be used to estimate the median duration of TTPP1. A two-sided 95% CI will be provided for this estimate. The 25th and 75th percentiles, and the range (minimum, maximum) will be presented as well. The range will be determined including censored observations. Estimated Kaplan-Meier curve will be plotted.

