7.4.2.7 Radiographic Progression-Free Survival (rPFS)

The rPFS is defined as the time from randomization to the first objective evidence of radiographic disease progression assessed by the blinded independent central review facility or on-study death, defined as death within 28 days after treatment discontinuation, whichever occurs first. rPFS will be assessed in the ITT population. Radiographic disease progression will include soft tissue disease progression and confirmed bone disease progression. The censoring rules are shown in Table 7-1. The analysis of rPFS will be presented by planned treatment group for subjects that having least one distant metastasis at baseline in ITT population.

rPFS will be assessed using the same method as that with TTPP1. i.e. Stratified log-rank test and unstratified cox regression will be applied to rPFS and estimate the distribution using Kaplan-Meier method.

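### A subject who dies before any on-study scan is both an rPFS/MFS event and a day-0 censoring in the censoring table, and no text says which row prevails

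*Protocol*

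**What the plan says.** Two rows of the censoring table in Protocol 7.10 matter here. SAP Table 7-1 carries both unchanged.

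- **No-scan row.** It covers "Subjects without the result of radiographic assessment at baseline or in observation period". Its rPFS and MFS cells read "Considered as censoring at randomization", with no condition attached.
- **Death row.** Its rPFS and MFS cells read "The event is considered to occur at the time of death". It does not require a scan.

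Both endpoints include death by definition. Protocol 5.3.2.1 runs rPFS to the time when "radiographic disease progression is observed or death of any cause during the study period, whichever occurs earlier". Protocol 5.3.2.2 says "MFS is defined as the period from randomization to new radiographic metastatic lesion or death of any cause during the study period". SAP 6.1.2 repeats the protocol's rPFS definition, but SAP 7.4.2.7 limits the death component to "on-study death, defined as death within 28 days after treatment discontinuation, whichever occurs first".

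The only ranking rule is in SAP 7.4.1, the TTPP1 section: "If a subject meets the criteria for more than one censoring rule, they will be censored with the earliest censoring date". For rPFS, SAP 7.4.2.7 says "rPFS will be assessed using the same method as that with TTPP1" and then spells that out as the stratified log-rank test, Cox regression and Kaplan–Meier estimation.

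**The concern.** The first scheduled on-study scan is at Day 85, with a window of 14 days either side. A subject who dies earlier, with no unscheduled or discontinuation scan, has no radiographic result in the observation period and has also died on study. One cell then gives an event on the date of death and the other a censoring on day 0.

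The no-scan row mirrors the row for subjects without PSA values. The PSA endpoints lose no event by that wording, because death is itself a censoring for them. For rPFS and MFS death is an event, so the same wording can erase one.

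A subject censored on day 0 enters no risk set. If the literal reading were programmed, early deaths would leave both numerator and denominator, the rPFS and MFS curves would be too high, and any arm with more early deaths would look better than it is. rPFS is a secondary endpoint with a stratified log-rank test. The trial is open-label, so the choice is better fixed in writing than left to programming.

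**Working it through.** **1. The plan's own figure.** The only sample-size calculation is for TTPP1 (Protocol 7.1). HR = 6/10.5 = 0.571. Events = 4 × (1.960 + 1.282)² / (ln 0.571)² = 134.2, rounded up to 135. The protocol's event probabilities are 0.85833 and 0.96615, mean 0.91224, so N per group = 135 / (2 × 0.91224) = 73.99, rounded up to 74. Both stated figures reproduce. This point does not touch them, because TTPP1 is judged on PSA. No event target is given for rPFS or MFS.

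**2. The two rows side by side.** Take a subject with a baseline scan who dies on Day 60, on treatment and unscanned since randomization.

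- No-scan row: censored at randomization.
- Death row: event on Day 60.
- Definitions (Protocol 5.3.2.1 and 5.3.2.2): event on Day 60.

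**3. Does anything rank them?** The SAP 7.4.1 sentence applies when several censoring rules are met. For rPFS and MFS the death row is an event rule, so the sentence does not decide between the two. It also sits in the TTPP1 section, and what SAP 7.4.2.7 expressly carries over to rPFS is the test, the model and the curve estimate. The conflict is left open.

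**4. How many subjects could be affected?** Inputs:

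- median overall survival M of 30.2 and 32.4 months, from the chemotherapy-naive study in Protocol 1.2.2.3;
- first scan at Day 85 ± 14 (Protocol section VI);
- 30.4375 days per month (SAP 7.1.1).

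Assuming a constant hazard, P(death by day d) = 1 − exp(−ln 2 × (d/30.4375)/M). Day 85 is 85/30.4375 = 2.793 months.

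- M = 30.2: 1 − exp(−0.0641) = 6.2%.
- M = 32.4: 1 − exp(−0.0597) = 5.8%.
- Over the scan window: from 4.9% (Day 71, M = 32.4) to 7.2% (Day 99, M = 30.2).

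This probably overstates early deaths. The same hazard gives 1 − exp(−ln 2 × 12/30.2) = 24% dead by 12 months (23% with M = 32.4), which fits poorly with a required life expectancy of at least 12 months. With assumed medians of 60 and 120 months, the Day 85 figure falls to 3.2% and 1.6%.

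The documents do not say how many subjects will be M1. If 60 to 140 of the 200 are (assumption), deaths by Day 85 in the rPFS set range from 60 × 0.016 = 1.0 to 140 × 0.062 = 8.7. Not all of these would meet both rows, because an unscheduled or discontinuation scan takes a subject out of the no-scan row. For MFS, which covers subjects without distant metastasis, the documents give no survival figure, so none is offered.

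**The case against.** The strongest reply is that the table works only if the death row prevails. The row for subjects without radiographic progression at cut-off also censors rPFS and MFS and also has no exception for death. Anyone who dies without progression falls in it. If a row without an exception could override the death row, no death would ever count and the death row would be empty. The definitions point the same way. This argument stands as interpretation: it shows which reading is sensible. It does not put that reading into the documents, and the no-scan cell remains an unconditional instruction with the opposite result.

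Three stronger readings are tempting, and the documents do not support them.

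- A reader might infer that the table makes no provision for death. It does, in the death row. The defect is an unranked overlap.
- A reader might infer that the SAP 7.4.1 tie-break selects randomization as the earliest date. It ranks censoring rules against each other and is silent on an event against a censoring.
- A reader might express the loss as a share of rPFS events, or name the arm that would gain. No expected rPFS event count, M1 split or imbalance in early deaths is given.

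It is also fair to say that MFS is exploratory and only described, and that few subjects are likely to be involved.

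**Conclusion.** The concern holds as an unresolved conflict between two stated rules, one of which gives a wrong result if applied literally. It affects rPFS and the exploratory endpoint MFS and leaves the primary analysis intact. About 6% dead by Day 85 is best taken as an upper figure at the nominal scan date. It rests on a constant hazard and on survival medians from another study. The range of roughly 1 to 9 rPFS subjects rests further on an assumed number with distant metastasis. The case for correcting it is that the rule contradicts the endpoint definitions and is nearly free to repair, not that the effect is large.

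One linked matter must be settled at the same time. For rPFS, the protocol and SAP 6.1.2 count any death in the study period, while SAP 7.4.2.7 counts only deaths within 28 days of stopping treatment. A subject who stops on Day 5 and dies unscanned on Day 60 is an event under the first and not under the second. Precedence for the death row is incomplete until it is clear which deaths qualify.

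**What to change.** 1. In Protocol 7.10 and SAP Table 7-1, add one sentence to the no-scan row: for rPFS and MFS, a death that qualifies as an event under the endpoint definition takes precedence and is counted on the date of death; censoring at randomization for a missing scan applies only to subjects without such a death.
2. Reconcile the rPFS death component across Protocol 5.3.2.1, SAP 6.1.2 and SAP 7.4.2.7, so that one definition says which deaths qualify. State how a death after stopping treatment relates to the table's discontinuation row, which censors rPFS and MFS at the last scan before discontinuation.

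The cost is a sentence in each table and one aligned definition, with no new data, visits or sample-size change. The SAP requires departures from its planned analyses to be justified in the clinical study report. If its text can no longer be amended before hard lock, the rule applied should be stated there, with the number of subjects who met both rows in each group.
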